#### 7.9.4 Laboratory Results

Laboratory test results will be presented in conventional units. Serum chemistry, hematology, and urinalysis parameters will be collected at pre-treatment, 6 hours post-treatment and at 8 and 90 days post-treatment for the initial icatibant treatment.

Observed values and changes from pre-treatment will be summarized by study time-point. Laboratory test results will be classified according to the reference ranges and clinical significance as determined by the investigator. The number of subjects with a non-missing result, and the number and percentage of subjects with a clinically significant result less than the lower limit of normal, non-clinically significant result less than the lower limit of normal, within the normal range, non-clinically significant result more than the upper limit of normal, and clinically significant result more than the upper limit of normal will be summarized by study time point. If more than one laboratory result is reported per study time point per parameter, the result yielding the most severe classification will be selected for analysis. Listings of abnormal results and records with missing reference ranges (eliminated from the summary analysis), as well as results of the same laboratory parameter for the subject across all study time points, will be presented.

Laboratory parameters collected are listed below.

##### Serum Chemistry:

Albumin, Alkaline phosphatase, Alanine aminotransferase, Aspartate aminotransferase, Calcium, Carbon dioxide, Chloride, Creatinine, Creatine kinase, Gamma-glutamyl transferase, Glucose, Lactate dehydrogenase, Phosphorus, Potassium, Sodium, Total bilirubin.

##### Hematology:

Hematocrit, Hemoglobin, Mean corpuscular hemoglobin, Mean corpuscular hemoglobin concentration, Mean corpuscular volume, Platelet count, Red blood cell count, White blood cell count with differential.

##### Urinalysis:

Appearance, Bilirubin, Color, Glucose, Ketones, Nitrite, Occult blood, pH, Protein, Specific gravity.

#### 7.9.5 Electrocardiogram (ECG)

ECGs will be performed at screening and at 6 hours (or 8 hours for subjects who did not have complete resolution of HAE symptoms at 6 hours) post-treatment for the initial icatibant treatment. ECG results (abnormal or normal) will be summarized by study time point. Listings of treatment-emergent abnormalities, as well as results for the subject across all study time points, will be presented.

### 7.9.6 Vital Signs

Vital signs (temperature [°C], pulse [bpm], blood pressure [systolic and diastolic, mmHg], and respiration [per min]) will be collected at screening, pre-treatment, and 1 hour, 6 hours (or 8 hours for subjects who did not have complete resolution of HAE symptoms at 6 hours), 8 days and 90 days post-treatment for the initial icatibant treatment; and at pretreatment, 8 days and 90 days post-treatment for subsequent icatibant-treated attacks. Observed values and changes from pre-treatment will be summarized by study time-point.

### 7.9.7 Reproductive Hormone Assessments

Reproductive hormone levels will be measured in all subjects at pre-treatment, and 6 hours, 8 days and 90 days post-treatment for the initial icatibant treatment, and pretreatment, 8 days and 90 days post-treatment for subsequent icatibant-treated attacks. FSH, LH, estradiol, and progesterone will be summarized for females, and FSH, LH, and testosterone will be summarized for males. Observed values and changes from pre-treatment will be summarized by study time-point. The number and percentage of subjects with levels outside the normal range defined for their sex and pubertal status will be summarized by study time-point. Observations below the limit of detection will be considered abnormal if the lower limit of normal is not zero.

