7.6 Menstrual Cycle History

A menstrual cycle history will be determined historically for female subjects and will be recorded in the CRF. The timing of the blood sampling with respect to the menstrual cycle must be known to inform the interpretation of any potential changes in reproductive hormones in adolescent females, because of the normal cyclical rise and fall of reproductive hormones of the menstrual cycle.

Instructions for investigators:

To assist in this determination, investigators should obtain the following information and document in the CRF.

- Age of menarche
- Normal duration of menstrual flow
- Normal interval in between menstrual periods
- Date of last onset of bleeding
- Prospectively ask female subjects to write down subsequent dates of onset of bleeding and cessation of bleeding between Day 1 and Day 90
- Date of ovulation (sometimes called ovulation pain, mid-cycle pain or mittelschmerz) may also be documented if subjects can identify this feeling

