## 10.1.3 List of Data Listings

Listings	Data Listing Heading
16.2.1.1	Subject Disposition – Safety Population
16.2.1.2	Inclusion/Exclusion Criteria - All Population
16.2.2	Protocol Deviations – All Subjects
16.2.4.1	Demographic and Pre-treatment Characteristics - Safety Population
16.2.4.2.1	Medical History – Safety Population
16.2.4.2.2	HAE History – Safety Population
16.2.4.3.1	Concomitant Medications Other than Rescue Medication – Efficacy Population
16.2.4.3.2	Concomitant Medications Other than Rescue Medication - Safety Population
16.2.4.4.1	Rescue Medication - Efficacy Population
16.2.4.4.2	Rescue Medication - Safety Population
16.2.4.5	Details of Attack – Efficacy Population
16.2.5	Study Drug Administration – Safety Population
16.2.6.1	Symptom Score Assessed by Investigator – Efficacy Population
16.2.6.2	FLACC – Efficacy Population
16.2.6.3	FPS-R – Efficacy Population
16.2.6.4	Initial Symptom Relief Assessed by Investigator - Efficacy Population
16.2.7.1	Pre-Treatment Adverse Events - Safety Population
16.2.7.2	Treatment-Emergent Adverse Events - Safety Population
16.2.7.3	Treatment-Emergent Serious Adverse Events - Safety Population
16.2.7.4	Treatment-emergent Adverse Events Resulted in Study Discontinuation – Safety Population
16.2.7.5	Serious Adverse Events – All Subjects
16.2.7.6	Local Tolerability Assessed by Investigator – Safety Population
16.2.8.2.1	Clinical Laboratory Evaluations – Hematology - Safety Population
16.2.8.2.2	Abnormal Laboratory Values – Hematology - Safety Population
16.2.8.3.1	Clinical Laboratory Evaluations – Chemistry - Safety Population
16.2.8.3.2	Abnormal Laboratory Values – Chemistry - Safety Population
16.2.8.4.1	Clinical Laboratory Evaluations – Urinalysis - Safety Population
16.2.8.4.2	Abnormal Laboratory Values – Urinalysis - Safety Population
16.2.8.5.1	Reproductive Hormone Assessments - Safety Population
16.2.8.5.2	Reproductive Hormone Assessments deemed Abnormal - Safety Population
16.2.8.6	Urine Pregnancy Test (Females Only) - Safety Population
16.2.8.7	Immunogenicity - Safety Population
16.2.8.8.1	Electrocardiogram Data- Safety Population
16.2.8.8.2	Abnormal Electrocardiogram Data - Safety Population
16.2.8.9	Vital Signs - Safety Population
16.2.8.10	Menstrual Cycle History (Pubertal/Post-pubertal Females Only) - Safety Population

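### In post-menarchal girls the hormone tables ignore menstrual cycle phase, so normal cycling can mimic or obscure a drug effect at Day 8, Day 90 and repeat exposures

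*SAP*

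**What the plan says.** For the initial exposure, SAP 7.9.7 states: "Reproductive hormone levels will be measured in all subjects at pre-treatment, and 6 hours, 8 days and 90 days post-treatment for the initial icatibant treatment". Repeat exposures have pre-treatment, Day 8 and Day 90 samples only. On the analysis, "FSH, LH, estradiol, and progesterone will be summarized for females" and "Observed values and changes from pre-treatment will be summarized by study time-point". The categorical summary counts subjects with "levels outside the normal range defined for their sex and pubertal status will be summarized by study time-point".

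Protocol 7.6 covers the menstrual cycle: "The timing of the blood sampling with respect to the menstrual cycle must be known to inform the interpretation of any potential changes" in adolescent females, "because of the normal cyclical rise and fall of reproductive hormones of the menstrual cycle". It then collects age at menarche, usual cycle interval, the last onset of bleeding and prospective bleeding dates from Day 1 to Day 90. An ovulation date is optional.

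In the SAP these data appear once, as listing 16.2.8.10, "Menstrual Cycle History (Pubertal/Post-pubertal Females Only) - Safety Population". The female hormone tables, 14.3.13.5 to 14.3.13.8, name no phase variable. SAP 9.1, 9.6 and 9.7 plan no covariate adjustment, subgroup analysis or sensitivity analysis.

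**The concern.** Reproductive hormone levels are part of the primary safety endpoint and a stated objective, and Protocol 11.8 gives the role of bradykinin in reproductive development as the reason for the external monitoring board. Four features make cycle phase matter here.

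- The study is single-arm, so no control group shows what cycling alone would produce.
- Hormonal contraception is excluded, so post-menarchal girls are expected to cycle naturally.
- The pubertal/postpubertal group is Tanner II to V, so it can mix girls before and after menarche.
- For repeat exposures, Protocol 8.4.1 allows a baseline up to 6 months before treatment, so its cycle day need bear no relation to that of the follow-up samples.

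If phase is ignored, a change between two phases enters the change-from-baseline table as if it were a change over treatment. A range not specific to phase can flag a value that is normal for its phase, or pass one that is abnormal for it.

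**Working it through.** The plan states no figure to reproduce: the sample size is empirical, and no hormone standard deviation, range limits or number of post-menarchal girls is given. What can be checked is how often two scheduled samples fall in different phases.

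**Inputs from the documents.** Day 8 ± 1 is 7 days after Day 1 (6 to 8). Day 90 ± 7 is 89 days after Day 1 (82 to 96). The 6-hour sample is 0.25 day after dosing. The repeat-exposure baseline is up to 6 months before treatment (taken as 0 to 183 days).

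**Assumptions, not from the documents.** Every baseline cycle day is equally likely. The cycle has length L, with a 14-day luteal phase and the remaining L − 14 days follicular. Base case L = 28.

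**Formula.** For two samples s days apart, let r = s mod L. The share of girls whose samples fall in different phases is

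2 × min(r, L − r, 14, L − 14) / L.

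**Base case, L = 28.**

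| Sample | s | r | Share in different phases |
|---|---|---|---|
| 6 hours | 0.25 | 0.25 | 0.5/28 = 1.8% |
| Day 8, earliest | 6 | 6 | 12/28 = 43% |
| Day 8, nominal | 7 | 7 | 14/28 = 50% |
| Day 8, latest | 8 | 8 | 16/28 = 57% |
| Day 90, lowest in window | 84 | 0 | 0% |
| Day 90, nominal | 89 | 5 | 10/28 = 36% |
| Day 90, latest | 96 | 12 | 24/28 = 86% |

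Averaged over the 15 days of the Day 90 window, the share is 39%. For a repeat-exposure baseline taken 0 to 183 days before treatment, the average share between baseline and treatment day is 50%.

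**Other cycle lengths.** At Day 8 the share is 14/L: 67% (21 days), 58% (24), 44% (32), 40% (35) and 31% (45). At Day 90, averaged over the window, it is 42% (21), 73% (35) and 17% (45). At 6 hours it stays between about 1% and 2%.

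**Small groups.** If n girls are cycling, the chance that at least one pair is discordant is 1 − (1 − p)^n. At Day 8 with p = 0.50 this is 88% for n = 3, 97% for n = 5 and 99.9% for n = 10. The values of n are illustrative.

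**Direction.** If f is any hormone curve that repeats each cycle and baseline day d is uniform over the cycle, f(d + s) and f(d) have the same average, so the expected change is zero. Phase mismatch therefore widens the spread of individual changes without shifting their expected mean. In a handful of girls, a chance imbalance can still move the observed mean either way.

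**The case against.** A reader might infer that normal cycling will be reported as a drug effect, or that the Day 8 and Day 90 changes are mostly phase shifts. The documents do not support either. The shares above are probabilities of being in different phases, not hormone changes, and with a random baseline day the mean is not biased. The planned 20 or more pubertal/postpubertal subjects include both sexes and girls before menarche, so the affected group could be very small.

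A reader might also infer that the SAP contradicts the protocol. It does not: Protocol 7.6 asks that timing be known for interpretation, and Protocol 10.6 plans only tabular summaries, changes from baseline and flags for new abnormalities, with no mention of phase. The hormone listings and listing 16.2.8.10 would let a reader match values to cycle dates by hand.

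The 6-hour sample is a real strength. It is nearly phase-matched, and with an adult half-life of 1.4 hours (Protocol 1.2.1) it is the sample closest to drug exposure. Pre-treatment values are judged against the same ranges, so flag counts can be compared with baseline. The laboratory's ranges are not in the documents; all that can be said is that the SAP defines them by sex and pubertal status.

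These points limit the size of the problem and the wording, but they do not remove it. Hand-matching of listings is not a prespecified analysis. Repeat exposures have no 6-hour hormone sample. A baseline flag count does not show whether a newly flagged value in one girl reflects a change of phase.

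**Conclusion.** The point holds for post-menarchal females at Day 8, Day 90 and repeat exposures. The SAP leaves unused, except in a separate listing, the dates that the protocol collects to interpret these hormones. Under a 28-day cycle, a 14-day luteal phase and a random baseline day, about half of Day 8 pairs and 36% of nominal Day 90 pairs (0-86% over the window) cross phases. Cycling can therefore mimic or obscure a drug effect in the tables, through added noise and through range flags created or masked. It does not imply a systematic bias in mean change.

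The 6-hour change is little affected, although its range flag is equally blind to phase. Males, prepubertal children and pre-menarchal girls are outside the point. The absolute size cannot be stated, because the number of cycling girls and the hormone variability are not given. This is a gap worth closing before the final tables are run, not an error that invalidates the hormone analysis.

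**What to change.** Amend SAP 7.9.7 and its outputs as follows, keeping the planned overall summaries.

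1. Derive cycle day and phase for each hormone sample from the recorded bleeding dates, with unknown phase as its own category.
2. Present pre-menarchal and post-menarchal females separately.
3. Classify post-menarchal values against phase-specific laboratory ranges where phase is known.
4. Show change from pre-treatment for same-phase pairs, with different-phase and unknown-phase pairs shown separately.
5. Print cycle day and phase beside each value in listings 16.2.8.5.1 and 16.2.8.5.2.

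No new visits or blood samples are needed, but the cost is more than one derived variable. Phase-specific ranges must be obtained, and cells will be small. Some samples will be of unknown phase: the diary runs only to Day 90, so a later bleed to date the Day 90 sample is not assured, and ovulation dates are optional. Menstrual history at Day 8 is listed for subjects treated without an attack (Protocol 8.2.2) but not for initial or subsequent attacks (8.3.2, 8.4.3.1), so phase at those visits depends on the prospective bleeding dates.

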### 7.9.8 Pregnancy Test Results

Female subjects of childbearing potential will undergo pregnancy testing at screening, pre-treatment and 90 days post-treatment. A listing of pregnancy test results will be presented by site number, subject number, icatibant exposure number, and study time point.

### 7.9.9 Concomitant Medication

Concomitant medications will be coded using the WHO Drug Dictionary (Version 2011, Q4).

Concomitant medications administered after the treatment start and within 5 days from the treatment start will be summarized by icatibant exposure number, therapeutic class, and preferred term for the Efficacy Population and the Safety Population. For medications with partial onset times, non-missing date parts will be used to determine if the medication qualifies as concomitant. If it cannot be definitively determined that a concomitant medication was used within 5 days from treatment start then it will be included in the summary.

### 7.9.10 Rescue Medication

Rescue medications will be coded using the WHO Drug Dictionary (Version 2011, Q4).

Rescue therapy is any medication used after the administration of icatibant which, in the opinion of the investigator, is immediately necessary to alleviate acute symptoms which are judged by the investigator as resultant from the current HAE attack.

Repeat administration of icatibant for the treatment of a single attack is not allowed in this study.

Antihistamines and corticosteroids are considered ineffective for the alleviation of an acute HAE attack. If administered during an acute attack that occurs during the study, they should be recorded as concomitant medications but will not be considered rescue medications.

Rescue medications administered after the treatment start and within 48+4 hours after the treatment start will be summarized by icatibant exposure number, therapeutic class, and preferred term for the Efficacy Population and the Safety Population. For medications with partial onset times, non-missing date parts will be used to determine if the rescue medication was used within 3 days of treatment. If it cannot be definitely determined that the rescue medication was used within 3 days of treatment, the rescue medication will be excluded from the summary. See Section [10.2.14](#) for the detailed definition of rescue medication.

**8. CHANGES IN THE CONDUCT OF THE STUDY OR PLANED ANALYSES**

**8.1 Changes in the Conduct of the Study**

There was no change in the conduct of the study.

**8.2 Changes from the Analyses Planned in the Protocol**

There was no change from the analyses planned in the protocol.

## **9. STATISTICAL/ANALYTIC ISSUES**

### **9.1 Adjustment for Covariates**

Given the small number of subjects treated in the study, no modelling approach will be performed to analyze the study data. Therefore, adjustment for covariates is not necessary.

### **9.2 Handling of Dropouts or Missing Data**

#### **9.2.1 Handling of Missing Data in Efficacy Assessments**

In general, a conservative approach that is unlikely to bias the results will be used to deal with missing data. Individual missing pretreatment scores, when the assessment was performed (i.e., other instrument-specific pretreatment scores are non-missing), will be assigned a value of mean value from the other available symptom scores when calculating the composite symptom scores at baseline.

Individual missing post-treatment scores, when the assessment was performed (i.e., other instrument-specific scores are non-missing), will be assigned the last non-missing value using last observation carried forward (LOCF). If the baseline observation is the last non-missing value it will be carried forward as well. This imputation method assumes that if an investigator did not rate a symptom at a particular assessment, then there was no change from the previous assessment.

#### **9.2.2 Handling of Missing Start Dates for Adverse Event Reporting**

For AEs with partial onset times, non-missing date parts will be used to determine if the AE is treatment-emergent or not. If a determination cannot be made using the non-missing date parts as to when the AE occurred relative to study drug administration then the AE will be classified as treatment-emergent.

### **9.3 Interim Analyses and Data Monitoring**

An interim analysis was performed when at least 10 prepubertal children and at least 20 adolescents have been enrolled in the study to support a regulatory filing fulfilling Shire's commitment in the Paediatric Investigation Plan (PIP) for Firazyr (EMEA-000408-PIP01-08-M05). Also, an independent DSMB was established to provide ongoing, independent review and assessment of the safety data, and to safeguard the interests and safety of the participating subjects in the study. Analysis of the data for DSMB review was conducted according to the DSMB Charter and DSMB SAP. Because no formal hypothesis testing was planned, multiplicity concerns regarding repeated analyses were not an issue.

#### **9.4 Multicenter Studies**

Data from all centers that participate in this protocol will be combined so that an adequate number of subjects will be available for analysis. Given the small number of subjects treated at each study site, no analysis on study center effects is planned.

#### **9.5 Multiple Comparisons/Multiplicity**

Given the small number of subjects treated in the study, no modelling approach will be performed to analyze the study data. Therefore, adjustment for multiple testing is not necessary.

#### **9.6 Examination of Subgroups and Interactions**

Given the small sample size of this study, no analysis is planned to examine subgroups.

#### **9.7 Sensitivity Analyses**

No sensitivity analysis is planned for this study.

## 10. APPENDICES

### 10.1 APPENDIX I: List of Statistical Outputs

#### 10.1.1 List of Statistical Tables

Table	Table Title
14.1	Demographic and Pre-treatment Characteristics
14.1.1.1	Subject Disposition by Study Population and Pubertal Status Stratification Group (All Subjects)
14.1.1.2	Subject Disposition by Study Population for Icatibant Exposure Number 1 (All Subjects)
14.1.1.3	Subject Disposition by Icatibant Exposure Number and Study Population for Icatibant Exposure Number 2 and 3 (All Subjects)
14.1.2.1	Demographics and Pre-treatment Characteristic by Pubertal Status Stratification Group (Efficacy Population)
14.1.2.2	Demographics and Pre-treatment Characteristic for Icatibant Exposure Number 1 (Efficacy Population)
14.1.2.3	Demographics and Pre-treatment Characteristic by Icatibant Exposure Number for Icatibant Exposure Number 2 and 3 (Efficacy Population)
14.1.2.4	Demographics and Pre-treatment Characteristic by Pubertal Status Stratification Group (Safety Population)
14.1.2.5	Demographics and Pre-treatment Characteristic for Icatibant Exposure Number 1 (Safety Population)
14.1.2.6	Demographics and Pre-treatment Characteristic by Icatibant Exposure Number for Icatibant Exposure Number 2 and 3 (Safety Population)
14.1.3.1	Concomitant Medications by Pubertal Status Stratification Group, Therapeutic Class, and Preferred Term (Efficacy Population)
14.1.3.2	Concomitant Medications by Therapeutic Class, and Preferred Term for Icatibant Exposure Number 1 (Efficacy Population)
14.1.3.3	Concomitant Medications by Icatibant Exposure Number, Therapeutic Class, and Preferred Term for Icatibant Exposure Number 2 and 3 (Efficacy Population)
14.1.3.4	Concomitant Medications by Pubertal Status Stratification Group, Therapeutic Class, and Preferred Term (Safety Population)
14.1.3.5	Concomitant Medications by Therapeutic Class, and Preferred Term for Icatibant Exposure Number 1 (Safety Population)
14.1.3.6	Concomitant Medications by Icatibant Exposure Number, Therapeutic Class, and Preferred Term for Icatibant Exposure Number 2 and 3 (Safety Population)
14.1.4.1	Rescue Medications by Pubertal Status Stratification Group, Therapeutic Class, and Preferred Term (Efficacy Population)
14.1.4.2	Rescue Medications by Therapeutic Class, and Preferred Term for Icatibant Exposure Number 1 (Efficacy Population)
14.1.4.3	Rescue Medications by Icatibant Exposure Number, Therapeutic Class, and Preferred Term for Icatibant Exposure Number 2 and 3 (Efficacy Population)
14.1.4.4	Rescue Medications by Pubertal Status Stratification Group, Therapeutic Class, and Preferred Term (Safety Population)
14.1.4.5	Rescue Medications by Therapeutic Class, and Preferred Term for Icatibant Exposure Number 1 (Safety Population)
14.1.4.6	Rescue Medications by Icatibant Exposure Number, Therapeutic Class, and Preferred

Table	Table Title
	Term for Icatibant Exposure Number 2 and 3 (Safety Population)
14.1.5.1	On-Study HAE Attack and Drug Exposure for Icatibant Exposure Number 1 (Efficacy Population)
14.1.5.2	On-Study HAE Attack and Drug Exposure by Icatibant Exposure Number for Icatibant Exposure Number 2 and 3 (Efficacy Population)
14.1.5.3	Drug Exposure for Icatibant Exposure Number 1 (Safety Population)
14.1.5.4	Drug Exposure by Icatibant Exposure Number for Icatibant Exposure 2 and 3 (Safety Population)
14.1.6.1	Medical History by Pubertal Status Stratification Group, System Organ Class, and Preferred Term (Efficacy Population)
14.1.6.2	Medical History by System Organ Class, and Preferred Term for Icatibant Exposure Number 1 (Efficacy Population)
14.1.6.3	Medical History by Icatibant Exposure Number, System Organ Class, and Preferred Term for Icatibant Exposure Number 2 and 3 (Efficacy Population)
14.1.6.4	Medical History by Pubertal Status Stratification Group, System Organ Class, and Preferred Term (Safety Population)
14.1.6.5	Medical History by System Organ Class, and Preferred Term for Icatibant Exposure Number 1 (Safety Population)
14.1.6.6	Medical History by Icatibant Exposure Number, System Organ Class, and Preferred Term for Icatibant Exposure Number 2 and 3 (Safety Population)
14.2	Efficacy
14.2.1.1	Time to Onset of Symptom Relief for Composite Investigator-Assessed Symptom Scores for Icatibant Exposure Number 1 (Efficacy Population)
14.2.1.2	Time to Onset of Symptom Relief for Composite Investigator-Assessed Symptom Scores for by Icatibant Exposure Number for Icatibant Exposure Number 2 and 3 (Efficacy Population)
14.2.2.1	Time to Minimum Symptoms for Composite Investigator-Assessed Symptom Scores for Icatibant Exposure Number 1 (Efficacy Population)
14.2.2.2	Time to Minimum Symptoms for Composite Investigator-Assessed Symptom Scores by Icatibant Exposure Number for Icatibant Exposure Number 2 and 3 (Efficacy Population)
14.2.3.1	Observed Value and Change from Pre-treatment in Composite Investigator-Assessed Symptom Score for Icatibant Exposure Number 1 (Efficacy Population)
14.2.3.2	Observed Value and Change from Pre-treatment in Composite Investigator-Assessed Symptom Score by Icatibant Exposure Number for Icatibant Exposure Number 2 and 3 (Efficacy Population)
14.2.4.1	Time to Individual Investigator-Assessed Symptom Relief for Icatibant Exposure Number 1 (Efficacy Population)
14.2.4.2	Time to Individual Investigator-Assessed Symptom Relief by Icantibant Exposure Number for for Icatibant Exposure Number 2 and 3 (Efficacy Population)
14.2.4.3	Individual Investigator-Assessed Symptom Scores for Icatibant Exposure Number 1 (Efficacy Population)
14.2.4.4	Individual Investigator-Assessed Symptom Scores by Icatibant Exposure Number for Icatibant Exposure Number 2 and 3 (Efficacy Population)
14.2.4.5	Individual Investigator-Assessed Symptom Score Shifts Relative to Pre-treatment value for Icatibant Exposure Number 1 (Efficacy Population)
14.2.4.6	Individual Investigator-Assessed Symptom Score Shifts Relative to Pre-treatment value

Table	Table Title
	by Icatibant Exposure Number for Icatibant Exposure Number 2 and 3 (Efficacy Population)
14.2.4.7	Individual Investigator-Assessed Symptom Score Shifts Relative to 2 hr-post treatment value for Icatibant Exposure Number 1 (Efficacy Population)
14.2.4.8	Individual Investigator-Assessed Symptom Score Shifts Relative to 2 hr-post treatment value by Icatibant Exposure Number for Icatibant Exposure Number 2 and 3 (Efficacy Population)
14.2.5.1	Time to Onset of Symptom Relief for FPS-R Scores for Icatibant Exposure Number 1 (Subjects from Efficacy Population with FPS-R data)
14.2.5.2	Time to Onset of Symptom Relief for FPS-R Scores by Icatibant Exposure Number for Icatibant Exposure Number 2 and 3 (Subjects from Efficacy Population with FPS-R data)
14.2.5.3	Time to Minimum Symptom for FPS-R Scores for Icatibant Exposure Number 1 (Subjects from Efficacy Population with FPS-R data)
14.2.5.4	Time to Minimum Symptom for FPS-R Scores by Icatibant Exposure Number for Icatibant Exposure Number 2 and 3 (Subjects from Efficacy Population with FPS-R data)
14.2.5.5	Observed Value and Change from Pre-treatment in FPS-R Score for Icatibant Exposure Number 1 (Subjects from Efficacy Population with FPS-R data)
14.2.5.6	Observed Value and Change from Pre-treatment in FPS-R Score by Icatibant Exposure Number for Icatibant Exposure Number 2 and 3 (Subjects from Efficacy Population with FPS-R data)
14.2.6.1	Time to Onset of Symptom Relief for FLACC Scores by Pubertal Status Stratification Group (Subjects from Efficacy Population with FLACC data)
14.2.6.2	Time to Minimum Symptom for FLACC Scores by Pubertal Status Stratification Group (Subjects from Efficacy Population with FPS-R data)
14.2.6.3	Observed Value and Change from Pre-treatment in Total FLACC Pain Score by Pubertal Status Stratification Group (Subjects from Efficacy Population with FLACC data)
14.2.6.4	Individual FLACC Scores by Pubertal Status Stratification Group (Subjects from Efficacy Population with FLACC data)
14.2.7.1	Time to Use of Rescue Medication for the Treatment of Symptoms of the HAE Attack Following Study Drug Administration for Icatibant Exposure Number 1 (Efficacy Population)
14.2.7.2	Time to Use of Rescue Medication for the Treatment of Symptoms of the HAE Attack Following Study Drug Administration by Icatibant Exposure Number for Icatibant Exposure Number 2 and 3 (Efficacy Population)
14.2.8.1	Time to Initial Symptom Relief for Icatibant Exposure Number 1 (Efficacy Population)
14.2.8.2	Time to Initial Symptom Relief by Icatibant Exposure Number for Icatibant Exposure 2 and 3 (Efficacy Population)
14.2.9	Listing of Efficacy Results (Efficacy Population)
14.3	Safety
14.3.1.1	Summary of Treatment-Emergent Adverse Events by Pubertal Status Stratification Group (Safety Population)
14.3.1.2	Summary of Treatment-Emergent Adverse Events for Icatibant Exposure Number 1 (Safety Population)
14.3.1.3	Summary of Treatment-Emergent Adverse Events by Icatibant Exposure Number for Icatibant Exposure Number 2 and 3 (Safety Population)
14.3.2.1	Treatment-Emergent Adverse Events by System Organ Class, Preferred Term, and Pubertal Status Stratification Group (Safety Population)

Table	Table Title
14.3.2.2	Treatment-Emergent Adverse Events for Icatibant Exposure Number 1, System Organ Class and Preferred Term (Safety Population)
14.3.2.3	Treatment-Emergent Adverse Events by Icatibant Exposure Number, System Organ Class and Preferred Term for Icatibant Exposure Number 2 and 3 (Safety Population)
14.3.3.1	Treatment-Emergent Adverse Events by System Organ Class, Preferred Term, Maximum Severity, and Pubertal Status Stratification Group (Safety Population)
14.3.3.2	Treatment-Emergent Adverse Events by System Organ Class, Preferred Term, and Maximum Severity for Icatibant Exposure Number 1 (Safety Population)
14.3.3.3	Treatment-Emergent Adverse Events by Icatibant Exposure Number, System Organ Class, Preferred Term, and Maximum Severity for Icatibant Exposure Number 2 and 3 (Safety Population)
14.3.4.1	Treatment-Emergent Adverse Events by System Organ Class, Preferred Term, Relationship to Study Drug, and Pubertal Status Stratification Group (Safety Population)
14.3.4.2	Treatment-Emergent Adverse Events by System Organ Class, Preferred Term, and Relationship to Study Drug for Icatibant Exposure Number 1 (Safety Population)
14.3.4.3	Treatment-Emergent Adverse Events by Icatibant Exposure Number, System Organ Class, Preferred Term, and Relationship to Study Drug for Icatibant Exposure Number 2 and 3 (Safety Population)
14.3.5.1	Treatment-Emergent SAE by System Organ Class, Preferred Term, and Pubertal Status Stratification Group (Safety Population)
14.3.5.2	Treatment-Emergent SAE by System Organ Class and Preferred Term for Icatibant Exposure Number 1 - Safety Population (Safety Population)
14.3.5.3	Treatment-Emergent SAE by Icatibant Exposure Number, System Organ Class, and Preferred Term for Icatibant Exposure Number 2 and 3 - Safety Population (Safety Population)
14.3.6.1	Injection Site Reactions (ISR) for Icatibant Exposure Number 1 (Safety Population)
14.3.6.2	Injection Site Reactions (ISR) by Icatibant Exposure Number for Icatibant Exposure Number 2 and 3 (Safety Population)
14.3.6.3	Injection Site Reactions by Severity and Study Time Point for Icatibant Exposure Number 1 (Safety Population)
14.3.6.4	Injection Site Reactions by Icatibant Exposure Number, Severity, and Study Time Point for Icatibant Exposure 2 and 3 (Safety Population)
14.3.7.1	Anti-Icatibant Antibodies for Icatibant Exposure Number (Safety Population)
14.3.7.2	Anti-Icatibant Antibodies by Icatibant Exposure Number for Icatibant Exposure Number 2 and 3 (Safety Population)
14.3.8.1	Serum Chemistry Laboratory Values: Actual Value and Change from Pre-treatment by Study Time Point for Icatibant Exposure Number 1 (Safety Population)
14.3.8.2	Serum Chemistry Laboratory Values: Actual Value and Change from Pre-treatment by Icatibant Exposure Number and Study Time Point for Icatibant Exposure Number 2 and 3 (Safety Population)
14.3.8.3	Serum Chemistry Laboratory Values: Categorical Clinical Laboratory Results for Icatibant Exposure Number 1 (Safety Population)
14.3.8.4	Serum Chemistry Laboratory Values: Categorical Clinical Laboratory Results by Icatibant Exposure Number for Icatibant Exposure Number 2 and 3 (Safety Population)
14.3.9.1	Hematology Laboratory Values: Actual Value and Change from Pre-treatment by Study Time Point for Icatibant Exposure Number 1 (Safety Population)
14.3.9.2	Hematology Laboratory Values: Actual Value and Change from Pre-treatment by

Table	Table Title
	Icatibant Exposure Number and Study Time Point for Icatibant Exposure Number 2 and 3 (Safety Population)
14.3.9.3	Hematology Laboratory Values: Categorical Clinical Laboratory Results for Icatibant Exposure Number 1 (Safety Population)
14.3.9.4	Hematology Laboratory Values: Categorical Clinical Laboratory Results by Icatibant Exposure Number for Icatibant Exposure Number 2 and 3 (Safety Population)
14.3.10.1	Urinalysis Values: Actual Value and Change from Pre-treatment by Study Time Point for Icatibant Exposure Number 1 (Safety Population)
14.3.10.2	Urinalysis Values: Actual Value and Change from Pre-treatment by Icatibant Exposure Number and Study Time Point for Icatibant Exposure Number 2 and 3 (Safety Population)
14.3.10.3	Urinalysis Values: Categorical Clinical Laboratory Results for Icatibant Exposure Number 1 (Safety Population)
14.3.10.4	Urinalysis Values: Categorical Clinical Laboratory Results by Icatibant Exposure Number for Icatibant Exposure Number 2 and 3 (Safety Population)
14.3.11.1	ECG Results by Study Time point for Icatibant Exposure Number 1 (Safety Population)
14.3.11.2	ECG Results by Study Time point by Icatibant Exposure Number for Icatibant Exposure Number 2 and 3 (Safety Population)
14.3.12.1	Vital Signs: Actual Value and Change from Pre-treatment by Study Time point for Icatibant Exposure Number 1 (Safety Population)
14.3.12.2	Vital Signs: Actual Value and Change from Pre-treatment by Icatibant Exposure Number and Study Time point for Icatibant Exposure Number 2 and 3 (Safety Population)
14.3.13.1	Reproductive Hormone Assessments (Males): Actual Value and Change from Pre-treatment by Study Time point for Icatibant Exposure Number 1 (Safety Population)
14.3.13.2	Reproductive Hormone Assessments (Males): Actual Value and Change from Pre-treatment by Icatibant Exposure Number and Study Time point for Icatibant Exposure Number 2 and 3 (Safety Population)
14.3.13.3	Reproductive Hormone Assessments (Males): Categorized According to Reference Ranges by Study Time point for Icatibant Exposure Number 1 (Safety Population)
14.3.13.4	Reproductive Hormone Assessments (Males): Categorized According to Reference Ranges by Icatibant Exposure Number and Study Time point for Icatibant Exposure Number 2 and 3 (Safety Population)
14.3.13.5	Reproductive Hormone Assessments (Females): Actual Value and Change from Pre-treatment by Study Time point for Icatibant Exposure Number 1 (Safety Population)
14.3.13.6	Reproductive Hormone Assessments (Females): Actual Value and Change from Pre-treatment by Icatibant Exposure Number and Study Time point for Icatibant Exposure Number 2 and 3 (Safety Population)
14.3.13.7	Reproductive Hormone Assessments (Females): Categorized According to Reference Ranges by Study Time point for Icatibant Exposure Number 1 (Safety Population)
14.3.13.8	Reproductive Hormone Assessments (Females): Categorized According to Reference Ranges by Icatibant Exposure Number and Study Time point for Icatibant Exposure Number 2 and 3 (Safety Population)

